2.2 Analysis sets

The following analysis sets are defined:

- The randomized (RAN) set will consist of all patients who were assigned a randomization number, regardless of whether or not they actually received study medication. Patients in RAN will be analyzed according to the treatment they were randomized to. The RAN set will be used for a summary of patient disposition, demographics and baseline characteristics.
- The Full Analysis Set (FAS) will consist of all patients in the RAN set who received at least one dose of study medication. Following the intent-to-treat principle, patients will be analyzed according to the treatment they were assigned to at randomization. The FAS will be used in the analysis of all efficacy variables.
- The Per-Protocol set (PPS) will include all patients in the FAS who did not have any major protocol deviations. Major protocol deviations will be defined in the validation analysis plan prior to database lock and the un-blinding of the study. The list of major protocol deviations is available in [Appendix 16.1.9](#). Patients will be analyzed according to the treatment they received. The PPS will be used for supportive analysis of the primary analysis only.
- The Safety Set will consist of all patients who received at least one dose of study medication including non-randomized patients who received study drug in error. Patients will be analyzed according to the treatment they received. If patients switch double-blind treatment during the study, they will be counted and analyzed only once according to their initial treatment. The safety set will be used in the analysis of all safety variables.

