2.6 Efficacy evaluation

All efficacy analyses will be performed on the FAS and selected analyses will be repeated on the PPS. Measurements made after patients discontinue randomized treatment (off-treatment measures) will not be used for any efficacy evaluation.

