2.6.1 Analysis of the primary and key secondary variables

The primary objective is to demonstrate the superiority of either QMF149 150/160 µg to MF 400 µg or QMF149 150/320 µg to MF 800 µg in terms of trough FEV₁ after 26 weeks of treatment. The key secondary objective is to demonstrate the superiority of QMF149 (150/160 µg and 150/320 µg combined) to MF (400 and 800 µg combined) in terms of ACQ-7 after 26 weeks of treatment.

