2.6.1.2 Statistical model, hypothesis, and method of analysis

Primary variable

The primary objective to demonstrate superiority of either QMF149 150/160 µg to MF 400 µg or QMF149 150/320 µg to MF 800 µg in terms of trough FEV₁ after 26 weeks of treatment will be evaluated by testing the following null hypotheses (H₀) versus the alternative hypotheses (H_a):

H₀₁: QMF149 150/160 µg is equal to MF 400 µg

versus

H_{a1}: QMF149 150/160 µg is not equal to MF 400 µg

and

H₀₂: QMF149 150/320 µg is equal to MF 800 µg

versus

H_{a2}: QMF149 150/320 µg is not equal to MF 800 µg

The primary variable, trough FEV₁ at Week 26, will be analyzed using a mixed model for repeated measures (MMRM) on the FAS. The model will contain treatment, age group (12 to 17, or ≥ 18 years), region (Eastern Europe, Western Europe, India, Japan, other Asia, rest of world), visit (Days 2, 184, and 365), and treatment-by-visit interaction as fixed effects with baseline FEV₁ measurement, baseline-by-visit interaction, FEV₁ prior to inhalation and FEV₁ within 15 to 30 min post inhalation of salbutamol/albuterol (components of short acting beta-2 agonist (SABA) reversibility) as covariates, and center nested within region as a random effect. The within-patient correlation will be modeled using an unstructured covariance matrix in the mixed model. The Kenward-Roger approximation will be used to estimate denominator degrees of freedom (Kenward and Roger, 1997).

For the primary analysis, if the model does not converge, data only up to week 26 (i.e., Days 2 and 184) will be used (with unstructured covariance matrix). If still the model fails to converge, compound symmetry covariance matrix will be used. If model still does not converge, the random effects of center will be removed. For the final analysis, if the model does not converge with unstructured covariance matrix, the compound symmetry covariance matrix will be used in the mixed model. If still the model does not converge, the random effects of center will be removed. For both analyses, if the model converges after removing the random center effects, the original model without random center effects will be re-assessed. If the final model for the primary analysis converges without Week 52 data, only summary statistics will be provided for Week 52 data analysis. Restricted maximum likelihood method will be used.

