2.6.1.4 Supportive analyses for the primary objective

As supportive analysis, the same MMRM used in the primary analysis will be also performed on the PPS to assess the treatment effect in protocol adherers.

In addition, the same primary MMRM on the FAS will be performed including all spirometric measures irrespective of single depot corticosteroid injection, other systemic corticosteroid use, or rescue medication use. However, measures taken outside of the 22 – 25 hour post-evening dose window for o.d. regimens (or 8 - 13 hour post-morning dose window for b.i.d. regimens) will be excluded.

As a further sensitivity analysis, a so-called 'tipping point analysis' will be performed for the primary endpoint to evaluate the impact of a deviation from the MAR assumption. The delta-adjusting approach described in Ratitch et al (2013) will be used to find the tipping point, in a spectrum of conservative missing not at random (MNAR) assumptions, at which conclusions change from being favorable to QMF149 to being unfavorable. After such a tipping point is determined, clinical judgment can be applied as to the plausibility of the assumptions underlying this tipping point. This methodology would provide a good picture of what it would take to overturn study conclusions on the basis of varying assumptions about missing data. The basic idea is to first impute the missing Week 26 values using the multiple imputation (MI) method based on the missing at random (MAR) assumption. The imputed Week 26 values for the QMF149 arms are then adjusted by a delta value. A detailed description of the analysis steps is provided in [Appendix 16.1.9](#).

The following ██████████ subgroup analyses for trough FEV₁ using MMRM will be performed (using the appropriate interaction term in the model and additional covariate as a fixed effect if necessary) for the FAS to explore the treatment effect in:

- Age group (12 to 17 years, ≥ 18 years)
- Race (Caucasian, Asian, Black and other)
- Sex (male, female)
- History of asthma exacerbation in the 12 months prior to screening (Yes, No)
- Patients' prior therapies before run-in period (medium dose of ICS, high dose of ICS, and low dose ICS/LABA; see Appendix 11 of the study protocol for the definition of ICS dose levels)
- Pre-bronchodilator FEV₁ in % of predicted FEV₁ at run-in visit 101 (50% to < 60%, 60% to < 85%)
- ACQ-7 at baseline (1.5 - < 2, 2 - < 2.5, ≥ 2.5)

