2.6.2 Analysis of secondary variables

Three treatment comparisons will be performed on all secondary variables: 1) QMF149 150/160 µg vs. MF 400 µg, 2) QMF149 150/320 vs MF 800 µg, 3) QMF149 150/320 µg vs. salmeterol xinafoate /fluticasone propionate 50/500 µg b.i.d.. The third comparison will be done on the key secondary variable too and on the primary variable as described below.

2.6.2.1 Comparison of QMF149 150/320 µg vs salmeterol xinafoate/fluticasone propionate 50/500 µg b.i.d. in term of trough FEV₁ at Week 26

QMF149 150/320 µg will be compared to active control (salmeterol xinafoate /fluticasone propionate 50/500 µg b.i.d.) for non-inferiority and – if non-inferiority is shown – for superiority on the primary endpoint. The same MMRM as specified above will be applied. The margin for non-inferiority is defined as 90 mL (see Appendix 12 of the study protocol for the estimation of non-inferiority margin). The result will be interpreted based on the two-sided 95% confidence interval (CI) of the treatment difference QMF149 – active control. The lower bound of the 95% CI is the difference that can be ruled out, i.e., if the lower bound of the 95% CI is larger than the non-inferiority margin of -90 mL, then QMF149 150/320 µg can be considered non-inferior to active control, and if the lower bound of the 95% CI is greater than 0, then QMF149 150/320 µg can be considered superior to active control with regard to trough FEV₁ at Week 26. Note that the comparison versus active control is not part of the confirmatory testing strategy.

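### The Week 26 non-inferiority comparison with salmeterol/fluticasone has no per-protocol result, although the model that would supply it is already planned

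*SAP*

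**What the plan says.** SAP 2.2 assigns the analysis sets: "The FAS will be used in the analysis of all efficacy variables", and for the per-protocol set, "The PPS will be used for supportive analysis of the primary analysis only". Protocol 9.1 carries the same assignment. SAP 2.6 is looser: "All efficacy analyses will be performed on the FAS and selected analyses will be repeated on the PPS", without naming which ones.

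The only PPS efficacy analysis spelled out is in SAP 2.6.1.4, among the supportive analyses for the primary objective, where "the same MMRM used in the primary analysis will be also performed on the PPS". SAP 2.6.1 defines that objective as showing that QMF149, at one or other dose, beats MF at the matching dose level. Salmeterol/fluticasone is not part of it.

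The active-control comparison is in SAP 2.6.2.1 and protocol 9.5.1.1. For the model, the SAP says "The same MMRM as specified above will be applied". QMF149 150/320 µg may be considered non-inferior "if the lower bound of the 95% CI is larger than the non-inferiority margin of -90 mL". No second analysis set is named for this reading. Both documents add that the comparison lies outside the confirmatory testing strategy.

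**The concern.** In a superiority comparison, deviations that blur the arms usually work against the claim. In a non-inferiority comparison between two active arms they can work for it, because a difference moved toward zero moves away from the margin. A result in protocol adherers is therefore the usual companion to a full-set non-inferiority result.

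Here the PPS check is specified for QMF149 versus MF, where dilution is conservative, and not for the comparison where it may not be. At stake is how far a reader can rely on a non-inferiority statement that has a margin and a conclusion fixed in advance, in an analysis that SAP 2.9.2 says supports a marketing authorization filing.

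**Working it through.** **Inputs**
- SD 380 mL, effect 100 mL, 400 per arm, 10% dropout: SAP 2.10.
- 360 per arm completing 26 weeks: protocol section 4 (400 × 0.9).
- Margin -90 mL, two-sided 95% CI: SAP 2.6.2.1.
- Historical effect of the active control over placebo, lower limit 281 mL: protocol Appendix 12.
- Share of patients with deviations, and share kept in the PPS: not in the documents, so varied below.

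**The plan's own figures.** SE = 380 × √(2/360) = 28.3 mL. Power for one MF comparison is 94.2% at two-sided 0.05 and 90.1% at 0.025. Under the trimmed Simes steps, 0.901 + 0.041 × 0.942 = 94.0%, against the stated 94%. The preserved effect, (281 - 90)/281 = 68%, also reproduces. The documents state no power for the non-inferiority comparison.

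**Is the contrast available from the PPS model?** SAP 2.6.1.2 says: "The model will contain treatment, age group (12 to 17, or ≥ 18 years), region" and further terms, including treatment-by-visit. It does not list the levels of treatment. SAP 2.6.2.1 takes the active-control contrast from the same MMRM, so the salmeterol/fluticasone arm must be in it. SAP 2.6.1.4 refits that MMRM on the PPS. That the PPS fit can supply the contrast is an inference, but a safe one.

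**What the FAS analysis removes.** SAP 2.6 drops measurements after discontinuation of randomized treatment. SAP 2.6.1.1.1 sets FEV₁ to missing near rescue medication, systemic corticosteroids or a depot injection, and outside the dosing windows.

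**What it leaves in.** SAP 16.1.9.2 excludes the following from the PPS only:
- compliance failure affecting the data (OTH06);
- banned asthma medication (COMD01), which can include drugs in protocol Table 5-2, such as leukotriene antagonists or xanthines, that do not set FEV₁ to missing;
- ineligible patients, for example with ACQ below 1.5 (INCL05).

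**Illustration.** Suppose the true difference in adherent patients is exactly -90 mL, and a share x of FAS patients has no difference between the arms. The FAS difference is then -90(1 - x), and P(declare non-inferiority) = 1 - Φ(1.96 - 90x/28.3).

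| Assumed x | Shift (mL) | P(declare) |
|---|---|---|
| 0 | 0 | 2.5% |
| 5% | 4.5 | 3.6% |
| 10% | 9 | 5.0% |
| 20% | 18 | 9.3% |

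**Precision on the PPS.** At zero true difference, power = Φ(90/SE - 1.96).

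| Assumed share of the 360 kept | n per arm | CI half-width (mL) | Power |
|---|---|---|---|
| 100% (FAS) | 360 | 55.5 | 88.8% |
| 90% | 324 | 58.5 | 85.4% |
| 80% | 288 | 62.1 | 81.1% |
| 70% | 252 | 66.4 | 75.8% |
| 60% | 216 | 71.7 | 69.2% |

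80% power needs 280 per arm, or 280/360 = 78% retained.

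**The case against.** The case for leaving the plan alone has real substance.

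- **Status.** The comparison is not confirmatory. A reader might infer from the table above that the trial's type I error is inflated. The documents do not support that: the controlled family contains only the two trough FEV₁ hypotheses against MF and the ACQ-7 hypothesis.
- **The FAS analysis is not a plain intention-to-treat analysis.** It targets an on-treatment effect and removes much of what usually dilutes a comparison. Protocol 5.4.9 also requires study treatment to stop for prolonged prohibited treatment or non-compliant use of it, after which values leave the efficacy analysis. This stands, and it narrows the concern. It does not close it, because the SAP still expects patients with OTH06 or COMD01 in the FAS.
- **The PPS list is mostly about entry.** Of 39 codes that exclude from the PPS alone, about five (OTH04, OTH06, COMD01, WITH01, WITH02) concern conduct after randomization. The rest are mainly eligibility, washout or run-in deviations. These change the population, and nothing shows that they shrink the difference between two active arms. WITH01 and WITH02 depend on exacerbations during treatment, so the PPS can itself be biased in either direction.
- **The wording has some slack.** SAP 2.6 speaks of selected analyses, SAP 16.1.9.6 of all relevant contrasts, and SAP 2.9.2 uses primary analysis for the whole Week 26 readout. A sponsor could read the PPS contrast in. But SAP 2.2 is restrictive, the heading of SAP 2.6.1.4 is the primary objective, and no text assigns the contrast to the PPS.
- **The size is a boundary case.** If -90 mL were ruled out on a FAS diluted by 10% or 20%, the undiluted bounds would be -90/0.9 = -100 mL or -90/0.8 = -112.5 mL. These still preserve (281 - 100)/281 = 64% or (281 - 112.5)/281 = 60% of the historical lower limit.

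These points limit the weight of the concern. None is a reason to omit a result that the planned model can give.

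**Conclusion.** The gap is real and modest. A non-inferiority reading with a stated margin rests on the FAS alone because two passages confine the PPS to the superiority analysis. Some deviations that could favour non-inferiority remain in the FAS.

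The figures of 3.6%, 5.0% and 9.3% rest on SD 380 mL, 360 per arm, a true deficit exactly at the margin and an assumed dilution. They show the direction and scale of the risk and do not estimate its actual size in this trial.

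Two stronger conclusions are tempting and unsupported. One is that the FAS is known to be anti-conservative here: the documents give no deviation rate, and much of the dilution is already removed. The other is that non-inferiority should be claimed only if both sets agree. With 80% retained, power for such a joint rule could not exceed 81.1%, against 88.8% on the FAS, and the PPS lacks the full protection of randomization.

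**What to change.** - **SAP 2.2:** extend the use of the PPS to the Week 26 comparison with salmeterol/fluticasone.
- **SAP 2.6.2.1:** report the Day 184 difference, QMF149 150/320 µg minus salmeterol/fluticasone, and its 95% CI from the already planned PPS MMRM. Label it supportive and show it beside the FAS result. State any disagreement about excluding -90 mL when non-inferiority is interpreted.
- **SAP 2.6:** name the analyses that will be repeated on the PPS.
- **Protocol 9.1:** align the restriction, so that the two documents do not contradict each other.

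The cost is one extra contrast from a fitted model and one table row. No new patients or new model are needed. The PPS interval will be wider (half-width 62.1 mL against 55.5 mL if 80% are retained), so a PPS limit below -90 mL may reflect lost precision as well as a less favourable estimate. The interpretation should say which.

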2.3 Patient disposition, background and demographic characteristics

2.3.1 Patient disposition and protocol deviations

The number of patients will be summarized by region (i.e., Eastern Europe, Western Europe, India, Japan, Asia (other than India and Japan), rest of world), country and treatment group for the RAN set. Further, for each study epoch (i.e., screening, run-in, treatment phase, post treatment follow-up), the overall number of patients who entered, completed, and discontinued that phase will be summarized including the reasons for discontinuation of that phase.

The number of patients who completed the 52-week study treatment and who discontinued prematurely will be shown including the reasons for discontinuation of study treatment. In the Primary Analysis CSR, the number of patients who are ongoing at the time of interim database freeze will be presented. Time to premature treatment discontinuation will be displayed graphically for each treatment group using a Kaplan-Meier curve for the safety set. The date of premature treatment discontinuation is defined as the date of last dose of study medication. Patients who completed the study treatment will be censored at the date of last dose of study medication. In the interim analysis, patients who are ongoing at the time of interim database freeze will be censored at the Data Lock Point (DLP), which is defined as the date when all patients have completed at least Week 26 assessments or prematurely withdrawn from the study.

Number of patients with protocol deviations will be tabulated by category (e.g., selection criteria not met, prohibited concomitant medication, key procedures not performed as per protocol) and deviation.

The number of patients included in each analysis set will be tabulated, as well as the reasons for exclusions from analysis sets.

2.3.2 Demographics and baseline characteristics

Demographics and baseline characteristics will be summarized by treatment group using the RAN set. Summaries will include age, gender, race, ethnicity, height, weight, body mass index (BMI), relevant medical history, pre- and post-bronchodilator screening spirometry parameters: (FEV₁ in L and % of predicted FEV₁, FVC, FEV₁/FVC and FEF₂₅₋₇₅), FEV₁ reversibility (in L and %), duration of asthma, history of asthma exacerbations, prior asthma treatment, and smoking history.

Continuous variables will be summarized using descriptive statistics (number of non-missing data, mean, standard deviation, median, first and third quartiles, minimum, and maximum) and categorical variables will be summarized in terms of the number and percentage of patients in each category including a category for missing data if any.

Baseline is defined as the last available measurement before first dose of study drug.

No statistical analyses will be provided for baseline comparability among the treatment groups.

In addition, the following categorizations will be done:

- Age into 12 – 17 years, 18 - 64 years, and ≥ 65 years;
- BMI into ≤ 30.0 kg/m² and > 30.0 kg/m²;
- Duration of asthma into < 1 year, 1 - 5 years, $> 5 - 10$ years, $> 10 - 15$ years, $> 15 - 20$ years, and > 20 years;
- Number of asthma exacerbations in the 12 months prior to the start of the study that required treatment into 0, 1, > 1
- pre-bronchodilator FEV₁ into 50 - $< 60\%$, $60\% - < 85\%$ of predicted FEV₁
- ACQ-7 into < 1.5 , $1.5 - < 2$, $2 - < 2.5$, ≥ 2.5 (< 1.5 will be added in case of protocol deviations)
- prior asthma treatment into ICS medium dose, ICS high dose, ICS/LABA low dose, ICS/LABA other than low dose

Medical history will be coded with the Medical Dictionary for Regulatory Activities terminology (MedDRA) using the most actual version at the time of database lock. History/conditions will be summarized for the RAN set by primary system organ class and preferred term. Verbatim recorded history/conditions will be listed together with the coded terms, date of diagnosis/surgery and whether the problem was ongoing at start of the study.

2.4 Study medication

2.4.1 Duration of exposure

Duration of exposure to study treatment will be calculated as the number of days starting from the first dose date up to and inclusive the last dose date (ignoring the duration when study treatment may have been interrupted). The duration of exposure will be summarized by treatment for the safety set as a continuous variable with the standard descriptive statistics. In addition, the duration of exposure will be summarized with total patient years and the number (%) of patients who were exposed to study drug for each 1 - 29 days, 30 – 86 days, 87 – 183 days, 184 – 254 days, 255 – 365 days, and > 365 days.

In the interim analysis, patients who are ongoing at the time of interim database freeze will be considered as exposed until the DLP.

2.4.2 Compliance

Compliance will be calculated by counting the days where study drug was administered "As per protocol" according to the records on the Dosage Administration Record (DAR) Summary eCRF. The percentage of days divided by the days of exposure will be analyzed. To be counted as a day of compliance with study treatment, all five administrations, i.e., the Twisthaler and Accuhaler both in the morning and evening and the Concept 1 inhaler in the evening, have to be taken as per protocol. Compliance will be calculated by study treatment.

Compliance will be categorized into < 80 % and 80 % - 100 % and summarized by treatment for the safety set.

2.5 Prior and concomitant medication

Each medication, either an asthma or non-asthma medication, will have the start and end dates recorded on the eCRF. Separate tables will be provided for medications which were started and stopped prior to the first dose of study drug and medications which were taken concomitantly to the study drug (regardless of whether continued or started after the first dose of study drug).

Asthma medications will be summarized by the route of administration, the recorded pre-specified drug subcategories (including types of combination) and the coded preferred terms. The summary will be repeated by showing ingredients instead of preferred terms.

Non-asthma medications will be summarized by route of administration and preferred term.

Surgical and medical procedures (non-drug therapies) will be coded using MedDRA and presentations will be done by MedDRA primary system organ class and preferred term, separately for prior procedures and those after start of study drug.

Patients taking prohibited concomitant medications will be noted in the summary of protocol deviations.

All summarizations will be by treatment group in the Safety Set.

